# 8.3.1 Time period and frequency for collecting AE and SAE information

For Cohorts 1 to 10, all AEs and SAEs will be collected from the date of subject consent until discharge from the trial only IMP-related AEs and any SAEs will be collected.

For Cohorts 11 to 13 and 14, all AEs and SAEs will be collected from the date of subject consent until Visit 7 (the EoT Visit). From Visit 7 through 9 only IMP-related AEs, SAEs, and SARS-CoV-2 infections will be collected. After Visit 9 (e.g., Visits 10, 11, and 12) until the last scheduled FU Visit (i.e., when the subject is discharged from the trial), any SARS-CoV-2 infections and SAEs will be collected.

For subjects in Cohorts 11 to 13 who receive a non-trial SARS-CoV-2 vaccination, AEs/SAEs will be collected as specified above until the date when the subject was vaccinated with the non-trial SARS-CoV-2 vaccine. The AEs expected to be captured after non-trial SARS-CoV-2 vaccination are within the frame of post-marketing safety data reporting.

All SAEs (initial and follow-up reports) will be recorded and reported to the sponsor or designee within 24 h after becoming aware of the event, as indicated in Section 10.3.1.10.

Investigators are not obligated to actively seek AEs or SAEs after conclusion of the trial participation. However, if the investigator learns of any SAE, including a death, at any time after a trial subject has been discharged from the trial, and he/she considers the event to be reasonably related to the IMP administration or trial participation, the investigator must promptly notify the sponsor.

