#### **10.3.1.9 Documentation of particular situations**

#### AEs that are secondary to other events:

In general, AEs that are secondary to other events (e.g., cascade events or clinical sequelae) should be identified by their primary cause, with the exception of severe or serious secondary events. A medically significant secondary AE that is separated in time

from the initiating event should be documented as an independent AE in source data and CRF. For example:

- If vomiting results in mild dehydration with no additional treatment in a healthy adult, only vomiting should be documented as AE.
- If vomiting results in severe dehydration, both events should be documented as AEs separately.

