#### AEs of proven COVID-19 disease:

Any case of proven COVID-19 disease occurring till the last FU Visit should be reported as an SAE/AE. AEs which are rated as "moderate" or "severe" (according to the criteria provided in Section 10.3.1.7) will need to be reported as an SAE. If none of the other SAE definitions are deemed suitable, then the SAE criterion of being a "medically important event" should be applied (according to the definitions provided in Section 10.3.1.4). An SAE form should be completed, including follow-up information, as detailed in Section 10.3.1.10 such that an SAE report and narrative can be prepared and distributed.

BioNTech SE	Clinical Trial Protocol	Page 98 of 113
Confidential	including Amendments Nos. 01 to 09	Version: 13.0
	BNT162-01	Date: 12 JAN 2022

All mild cases of proven COVID-19 cases which do not correspond to seriousness criteria will be reported as AEs in the CRF.

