#### 6.4.3. Adverse Events

#### Definition

For detailed information on adverse events see section 10.3 of the protocol.

Adverse events (AEs) will be coded using the Updated Version MedDRA® 23.0 including specific terms for COVID-19 to get a system organ class (SOC) and preferred term (PT) for each AE.

A treatment emergent adverse event (TEAE) is defined as any AE with an onset after the first immunization (if the AE was absent before the first immunization) or worsened after the first immunization (if the AE was present before the first immunization). AEs with an onset date more than 28 days after the last immunization will be considered as treatment emergent only if assessed as related to IMP by the investigator. AEs that cannot be determined to not be treatment emergent due to missing date or time will be defined as TEAE.

Clarification: To clarify the definition in the protocol, AEs with an onset date at the date of the first immunization will only be considered as treatment emergent if the AE occurred after the first immunization.

The TEAEs will be evaluated for the following time intervals, clarifying and harmonizing the intervals defined in the protocol:

- Prime immunization up to boost immunization or day 28 (inclusive) after initial immunization (whatever comes first)
- Boost immunization up to day 28 (inclusive) after boost immunization
- All TEAEs (regardless of relationship assessment) occurring from

- Prime immunization up to day 28 after boost immunization (inclusive).
- If no boost immunization, up to 28 days (inclusive) after prime immunization
- All TEAEs assessed as related through visit 10.

The intervals starting or ending with an immunization, will start or end with the date and time of the immunization. TEAEs are assigned to the time intervals according to their start date and time. AEs with missing date will be assigned to each of the respective intervals if it cannot be ruled out, that it belongs to the time interval.

Deviating from the protocol, the time intervals including 7 days after each immunization will not be analyzed.

AEs will be evaluated for the following time interval 'After Day 28 after boost or after prime (if no boost)':

All AEs (regardless of relationship assessment) occurring

- After day 28 after boost immunization
- o If no boost immunization, after 28 days after prime immunization

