#### AEs

The number and percentage of subjects reporting at least one AE and the number of AEs will be summarized for the above defined time interval 'After Day 28 after boost or after prime (if no boost)' and the following AE types:

- Any AE
- Related AE
- Grade >=3 AE

- Related grade >=3 AE
- AEs with dose limiting toxicity (DLT)
- Any serious adverse event (SAE)
- Related SAE
- Deaths
- Any AEs linked to confirmed COVID-19 cases (defined as AEDECOD = 'COVID-19')

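### The SAP's late COVID-19 row promises linked AEs but counts one preferred term, so linked events coded to any other term fall outside it

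*SAP*

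**What the plan says.** SAP 6.4.3, under the subheading AEs, plans a table of subjects with at least one AE and of the number of AEs. These "will be summarized for the above defined time interval 'After Day 28 after boost or after prime (if no boost". The last row type is "Any AEs linked to confirmed COVID-19 cases (defined as AEDECOD = 'COVID-19". The SAP gives no term list, CRF flag or link to a test result for this row.

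The Definition part of the same section says that AEs are coded with the updated MedDRA 23.0, "including specific terms for COVID-19 to get a system organ class (SOC) and preferred term (PT) for each AE". It does not list those terms.

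The protocol sets out what reaches the database:

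- Section 8.3.1, for Cohorts 11 to 14: "From Visit 7 through 9 only IMP-related AEs, SAEs, and SARS-CoV-2 infections will be collected". After Visit 9, "any SARS-CoV-2 infections and SAEs will be collected".
- Section 10.3.1.9, on proven disease: "Any case of proven COVID-19 disease occurring till the last FU Visit should be reported as an SAE/AE".
- Section 10.3.1.9, on secondary events: these are identified by their primary cause, "with the exception of severe or serious secondary events". Its example records vomiting and a resulting severe dehydration as two AEs.

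**The concern.** The label and the derivation describe different quantities. Being linked to a case is a relation between events. Equality with one preferred term picks out only the record that names the disease. A programmer who follows the SAP exactly will leave out a separately recorded complication that the label includes. The same holds for a reported infection that the coder assigned to a different term.

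This matters because the row is the only COVID-19-specific summary planned for the long follow-up, which runs to Day 730 in Cohorts 11 to 13. Protocol 4.2 describes the immunocompromised adults of Cohort 13 as being at particular risk of severe complications, and Protocol 2.3.1 says that enhanced disease cannot yet be excluded. A reader of the report would take the row at its label.

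**Working it through.** The plan states no figure for this row, and no power or error-rate calculation bears on it. The check sets the derivation beside the recording and coding rules.

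1. **What the rule selects.** Only records in the late interval whose coded term equals COVID-19.

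2. **Separately recorded complications.** Protocol 10.3.1.9 excepts severe or serious secondary events from being folded into the primary cause. Such an event is its own AE and is coded to its own preferred term. It is linked to the case and fails the match. After Visit 7, Protocol 8.3.1 narrows collection in Cohorts 11 to 14 to IMP-related AEs, SAEs and infections. The complications at issue there are therefore mainly the serious ones.

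3. **Infections coded otherwise.** Protocol 8.3.1 refers to SARS-CoV-2 infections, while 10.3.1.9 refers to proven COVID-19 disease. The SAP does not say which term a reported infection receives. If it is not the exact term, the record is outside the row.

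4. **Subjects versus events.** The table reports both. An invented example shows the difference. Subject 1 has one AE coded COVID-19. Subject 2 has one AE coded COVID-19 plus a complication under another term. Subject 3 has an infection under another term only.
   - Exact match: subjects 1 and 2, with 1 + 1 = 2 AEs.
   - Grouping by link to a case: subjects 1, 2 and 3, with 1 + 2 + 1 = 4 AEs.

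   Subject 2 is counted either way and only the AE count is short. Subject 3 is the only kind of subject lost. The example shows the mechanism and says nothing about frequency.

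5. **Whether another summary fills the gap.** An AE starting more than 28 days after the last dose is a TEAE only if assessed as related (SAP 6.4.3; Protocol 10.3.1). The tables by preferred term within SOC, and the summary of AESIs, cover TEAEs only. A late unrelated infection or complication thus appears in no table by preferred term. It does appear in the Any AE row, in the Grade 3 or higher, SAE and Deaths rows where it qualifies, and in the AE and SAE listings. In those rows it is pooled with events that have nothing to do with COVID-19.

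6. **Size.** The documents give no number of cases, no list of the available COVID-19 terms and no coded terms. The undercount cannot be calculated.

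**The case against.** The strongest reply is that the row will usually be right. Protocol 10.3.1.7 asks for the diagnosis, not the symptoms, and 10.3.1.9 folds non-severe sequelae into the primary cause, so an ordinary symptomatic case should carry the exact term. Section 10.3.1.9 directs the reporting of proven cases, so confirmation is largely dealt with when the AE is recorded. The plural in the SAP's dictionary description does not show that several preferred terms for confirmed infection exist. COVID-19 incidence is not a primary or secondary endpoint, no hypothesis is tested, and the definition is explicit and reproducible. All of this stands. It limits the likely size of the undercount but does not make the rule match its label.

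Three stronger readings are tempting but are not supported:

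- **That asymptomatic infections are lost.** Protocol Tables 6 to 9 place antibody testing at Visit 0 and the swab at Day -1 or Visit 1. Section 8.2.10 adds ad hoc antibody testing for subjects with suggestive symptoms. The trial does not look systematically for asymptomatic infection, and the term that a reported one would receive is unknown.
- **That the severity of cases is understated.** The row reports no severity. Moderate and severe proven cases are reported as SAEs with a narrative, and complications enter the other rows of the same table where they qualify. What is missing is the link to the case.
- **That a number of missed subjects can be given.** Any such number needs an assumed infection rate and an assumed share coded elsewhere. The documents supply neither, and they do not exclude a share of zero.

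**Conclusion.** The point holds in a limited form. The row does not deliver the quantity it names. Separately recorded severe or serious complications fall outside it, as does any reported infection coded to another term. The number of linked AEs can therefore be understated. The number of subjects is understated only if none of a subject's AEs in the interval carries the exact term. The data remain in the general rows and the listings, but no other late summary identifies unrelated events as COVID-19.

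The size is undetermined and may be zero. The conclusion about complications assumes only that investigators follow the protocol's rule on secondary events. The conclusion about infections depends on coding that the documents do not show. The change should be made because it is cheap and the row stands alone. It does not affect any primary or secondary endpoint.

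**What to change.** Before the database snapshot, replace the single-term match with two rows, each labelled for what it counts:

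1. **Cases.** Subjects and AEs with any term on a fixed, versioned list of COVID-19 and SARS-CoV-2 infection preferred terms, drawn from the MedDRA version used and restricted to proven cases.
2. **Linked events.** Other AEs that medical review flags as secondary to such a case.

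The SAP already uses both devices. Section 6.4.3 excludes diary-based TEAEs by a versioned term list and relies on a CRF mark for AESIs, and section 5.2 already has a medical review before the snapshot.

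The cost is SAP wording, a term list and a small added review step. The AE assessments listed in Protocol 10.3.1.7 include no field tying an AE to a primary event, so the flag has to be assigned at review from the records already held. No new data collection is needed. Relabelling the row as the single preferred term would remove the mismatch at almost no cost, but linked events would still not be summarised.

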## AE listings

All AEs, AEs with DLT, AEs leading to early discontinuation and SAEs will be listed.

## TEAE figures

For each vaccine type, the most frequent TEAEs excluding TEAEs which are based on solicited reporting via diaries will be presented graphically using a bar plot for each time interval.

## 6.5. Secondary Analyses

Hereinafter, the secondary analyses for Part A are described.

Secondary endpoints are functional antibody responses, fold increase in functional antibody titers and the number of subjects with seroconversion. All secondary analyses will be performed using the IMM and possibly additionally the IMMPP population, see section 5.1.

All secondary analysis endpoints will be summarized by group (i.e. by vaccine type and cohort) and all cohorts combined for each type (cohort-total).

The functional antibody response will be assessed at the time points indicated in the tables 6, 7, 8 and 9 of the protocol.

## 6.5.1. Functional Antibody Response

## Definition

For data from VisMederi Srl, the functional antibody response is based on the virus neutralization test (VNT). For each subject and each time point two functional antibody titers will be determined, as each sample will be measured in replicate. The functional antibody response per subject and timepoint is defined as the geometric mean of the two functional antibody titers. In case more replicates are measured, the geometric mean of all measurements will be determined.

Other data on functional antibody response from Pearl River/UTMB, Pfizer will be presented as included in the SDTM dataset IS when requested by Pfizer

## Analysis

Functional antibody titers will be summarized using descriptive statistics for all time points. Additionally, GMT with 95% CI will be presented.

The functional antibody response will be listed.

Figure: For each vaccine type, functional antibody titers will be presented graphically displaying GMT with 95% CI at all time points (line plot).

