# 4.4 End of treatment (EoT) and end of trial definition

A trial subject is considered to have completed the trial if they have completed all planned visits as listed in the SoA, including all follow-up visits (see Section 1.3).

The EoT is defined as the date the last subject completed the EoT Visit (for BNT162c2 given SD Visit 6, for all cohorts with P/B dosing Visit 7).

BioNTech SE Confidential	Clinical Trial Protocol	Page 58 of 113
	including Amendments Nos. 01 to 09	Version: 13.0
	BNT162-01	Date: 12 JAN 2022

The end of trial is defined as the date when the last subject completed the last planned visit given in the SoA (see Section 1.3). The trial may end earlier if there are no remaining subjects from Cohorts 11 to 13 for the 2-year follow-up period (see Table 8); subjects who receive non-trial SARS-CoV-2 vaccinations will be discontinued.

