# 7.2 Trial subject discontinuation/withdrawal from the trial

A trial subject may withdraw from the trial at any time at his/her own request, or may be withdrawn at any time at the discretion of the investigator for safety, behavioral, compliance, or administrative reasons.

A trial subject in Cohort 11, 12, or 13 who receives a non-trial SARS-CoV-2 vaccination will be withdrawn from follow-up and discontinued from the BNT162-01 trial.

If the trial subject withdraws consent for data processing, the sponsor may retain and continue to use any data collected before such a withdrawal of consent.

If a trial subject withdraws from the trial, he/she may request destruction of any samples taken and not tested, and the investigator must document sample destruction in the Investigator's Site File (ISF).

If the trial subject withdraws consent or is permanently discontinued from the trial, the trial subject will be permanently discontinued both from IMP administration and from the trial at that time.

BioNTech SE	Clinical Trial Protocol	Page 69 of 113
Confidential	including Amendments Nos. 01 to 09	Version: 13.0
	BNT162-01	Date: 12 JAN 2022

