## 6. Statistical Analyses

## 6.1. General Considerations

The following described statistical analyses only refer to Part A of the study.

No formal statistical testing will be done.

Unless otherwise specified, analyses will be based on data pooled across all study sites.

Data assessed after the vaccination with a non-trial vaccine will be excluded from all statistical analyses.

Clarifications:

- Data assessed on the same day as the non-trial vaccination will remain in the analysis.
- If the date of non-trial vaccination is missing, but month and year information is available, data assessed after the last day of the respective month will be excluded from statistical analysis.

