## 6.1.1. Tables and Listings

#### Tables

In general, data will be summarized by groups (i.e., by vaccine type [BNT162a1, BNT162b1, BNT162b2, BNT162c2 SD and BNT162c2 P/B] and cohort) and all cohorts combined for each type (cohort-total). Furthermore, selected cohorts may be combined. The cohorts and cohort-total will be presented in columns and the different vaccine types in different tables.

There may be additional total columns for younger (18 to 55 years) and older (56 to 85 years) subjects.

Descriptive summary tables as well as figures will be based on scheduled visits.

Continuous variables will be summarized by group using the following descriptive statistics: number of subjects with non-missing data (n), mean, standard deviation (SD), median, minimum (min) and maximum (max).

Descriptive statistics of titer and fold increase of titer will additionally include geometric mean and its two-sided 95% confidence interval (CI). The geometric mean titer (GMT) is calculated as the mean of the logarithm of the functional antibody titers, back-transformed into the original scale. Two-sided CIs will be obtained by calculating CIs using t-distribution for the mean of the logarithmically transformed assay results and transforming the limits back to the original scale.

Geometric mean fold rise (GMFR) is calculated as the mean of the difference of logarithmically transformed assay results (post vaccination time point – pre vaccination time point) and back-transformed into the original scale. Two-sided CIs will be obtained by calculating CIs using Student's t-distribution for the mean difference of the logarithmically transformed assay results and transforming the limits back to the original scale.

Categorical variables will be summarized by group presenting absolute and relative frequencies (n and %) of subjects in each category (including the category 'missing' if applicable).

Percentages will be calculated based on the number of subjects in the respective analysis set (N) as denominator if not stated differently. Percentages may be presented with exact 95% Clopper-Pearson CIs.

SDs as well as CIs will only be calculated if values of at least 3 subjects are available.

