#### **Analysis Sets**

The SCR will be used for disposition. The SAF will be used for analysis of safety and adverse events data. Some analyses of the adverse events will be repeated using the SAFB if the SAF and the SAFB sets differ. The IMM will be used for the analysis of immunogenicity data. The analyses of all vaccines may be repeated using the IMMPP if the two analysis sets differ significantly. This will be decided at the data review meeting.

If subjects by accident receive two different doses or vaccines, they will switch the group and will be displayed for each immunization with the corresponding group. For combined analyses, subjects who received two different doses will be assigned to the lower dose. Subjects who receive different doses as per protocol will be presented in their respective group.

Data of subjects who failed to complete all visits of the study (dropout or withdrawal) will be reported as far as their data is available.

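### In Cohorts 11–13 the titer lines after Day 184 follow a changing set of subjects, so if departure is related to titer their slope mixes waning with changing composition

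*SAP*

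**What the plan says.** SAP 6.5.1 and 6.5.2 give visit-wise summaries. For titers: "Functional antibody titers will be summarized using descriptive statistics for all time points. Additionally, GMT with 95% CI will be presented". The interval is a one-sample interval at each visit (SAP 6.1.1, Tables): "Two-sided CIs will be obtained by calculating CIs using t-distribution for the mean of the logarithmically transformed assay results". Fold increase gets the matching GMFR with 95% CI. Both are drawn as line plots over all time points.

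The late visits enter through SAP 6.5: "The functional antibody response will be assessed at the time points indicated in the tables 6, 7, 8 and 9 of the protocol". Protocol Table 8 has immunogenicity draws for Cohorts 11–13 at Days 365, 547 and 730.

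The set of subjects shrinks by rule. Under Protocol 7.2 a subject in these cohorts "who receives a non-trial SARS-CoV-2 vaccination will be withdrawn from follow-up and discontinued from the BNT162-01 trial". A footnote to Table 8 stops immunogenicity sampling after such a vaccination. SAP 6.1 adds: "Data assessed after the vaccination with a non-trial vaccine will be excluded from all statistical analyses", with the exception "Data assessed on the same day as the non-trial vaccination will remain in the analysis". SAP 6.1.3 does not impute titers, and SAP 6.1.1 states: "Data of subjects who failed to complete all visits of the study (dropout or withdrawal) will be reported as far as their data is available".

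The protocol expects this to matter. Its synopsis says that approval of a third dose has affected the two-year follow-up, and Section 4.4 says: "The trial may end earlier if there are no remaining subjects from Cohorts 11 to 13 for the 2-year follow-up period".

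**The concern.** Protocol 4.2 gives long-term monitoring of the immune response as a purpose of Cohorts 11, 12 and 13, and a reader will take the plotted slope as durability. That reading is safe only if the subjects at Day 730 are, in titer, like those at Day 184.

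Age gives a concrete reason for doubt. Cohort 12 enrols 30 subjects in each of three age groups (18–55, 56–64, 65–85), and Protocol 2.3.1 reports lower antibody responses in older than in younger adults. If uptake of an outside vaccine differs by age, the titer mix of those remaining changes even when nobody's titer does. The SAP plans no within-subject summary after Day 50, no longitudinal model and no comparison of leavers with stayers.

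**Working it through.** **The plan's own figures.** The documents give no titer SD, waning rate or departure rate. The only statistical calculation is protocol Table 10 (for example 1 − 0.95^30 = 78.5% and 1 − 0.95^90 = 99.0%). It reproduces, but concerns adverse events and is not an input here.

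**Composition effect in Cohort 12.** Inputs: 30/30/30 by age group (protocol synopsis, Population). Assumptions: no waning; the two younger groups have equal titers; the 65–85 group has r times their titer, with r = 0.5 or 0.25. If s is the share of the 65–85 group among those present, the pooled GMT is proportional to r^s. At full enrolment s = 1/3, so the late GMT is multiplied by r^(s − 1/3).

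| Remaining (18–55 / 56–64 / 65–85) | s | r = 0.5 | r = 0.25 |
|---|---|---|---|
| 18/18/18 (40% of each group leave) | 1/3 | 1.00 | 1.00 |
| 24/24/6 (20%, 20%, 80% leave) | 6/54 = 1/9 | 1.17 | 1.36 |
| 30/30/0 (oldest group leaves) | 0 | 1.26 | 1.59 |
| 6/6/24 (80%, 80%, 20% leave) | 24/36 = 2/3 | 0.79 | 0.63 |

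The effect is therefore nil, +17% to +59%, or −21% to −37%, depending on who leaves.

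**When the line rises.** Observed fall = true fall ÷ inflation factor. With a true two-fold fall, factors of 1.17 and 1.59 give apparent falls of 2/1.17 = 1.71-fold and 2/1.59 = 1.26-fold. The line rises only if total waning is smaller than the factor, that is below 1.17- to 1.59-fold in these scenarios.

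**Departure depending directly on titer.** This was simulated with 90 subjects and 1,500 runs. Assumptions: SD 0.4 on log10 titer, assay noise 0.1, waning that varies between subjects, and about 45% leaving per interval at the mean titer. The log-odds of leaving fall by 1.5 per SD of the last titer in the selective rows. True titers never rise.

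| Waning per interval, departure | True GMT, Days 184/365/547/730 | Planned GMT |
|---|---|---|
| about 1.3-fold, unrelated to titer | 200/151/113/85 | 200/151/114/86 |
| about 1.3-fold, low titers leave | 199/149/112/85 | 199/234/252/263 |
| about 2-fold, low titers leave | 200/94/45/21 | 200/148/108/86 |

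The chance that the planned GMT rises from Day 184 to Day 365 was 0.00, 0.95 and 0.00 in the three rows.

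**GMFR.** At each visit GMFR is the stayers' GMT divided by the stayers' own baseline GMT. Composition cancels only if the groups' baselines differ by the same factor as their later titers, and nothing in the documents suggests that.

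**Within-subject ratio.** If every subject's titer falls w-fold after Day 50, each ratio to Day 50 is 1/w, and so is the geometric mean in any subset. A small example shows the same from one visit to the next: titers 20, 40, 80, 160, 320, 640 have GMT 113. If all fall 1.5-fold and the lowest three leave, the visit-wise GMT is 213 against a true 75. The stayers' ratio is 1/1.5 = 0.67, and 113 × 0.67 = 75.

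**The case against.** **Scope.** The listed secondary titer endpoints stop 162 days after the boost (Day 184). A reader might infer that the SAP fails a secondary endpoint; it does not. Days 365–730 enter only through the general reference to Table 8. Exploratory analyses sit in a separate biomarker SAP that was not available, so durability may be handled there. This stands as a limit on the point.

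**Selectivity is assumed.** No section links departure to titer or age, or gives a rate. Earlier departure of immunocompromised subjects could not shift the balance of immunocompromised against healthy within a cohort line, because they are all in Cohort 13. This also stands: the direction and size of the bias are unknown.

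**Pre-vaccination titers.** One might dismiss GMFR by saying that baselines sit at the detection limit. The documents do not say so: Protocol 8.10 provides for seropositive pre-immunization sera, and Protocol 8.2.10 uses the antibody screen as a baseline reference. The argument above does not need that premise.

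**Partial safeguards exist.** Tables report the number with data, titers are listed individually, discontinuations are summarised with reasons, and younger and older totals may be given. Attrition would thus be visible. But the age totals are optional and use two bands where Cohort 12 has three, the figures need not show n, and the per-protocol repeat (IMMPP) removes major deviators, not leavers. None of these separates waning from composition.

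**No hypothesis is tested.** True, so no error rate is at stake. The cost is a descriptive curve that can be misread.

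**Conclusion.** The point holds in conditional form. From Day 365 the planned GMT and GMFR lines in Cohorts 11–13 need not describe the course of any fixed group, and the planned outputs cannot show how much of the slope is waning. If the 65–85 group has titers two- to four-fold lower and leaves preferentially, the pooled Cohort 12 GMT is inflated by 17% to 59%. The bias is zero if departure is unrelated to titer and reverses if high-titer subjects leave first.

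A reader might go further and infer that waning will be understated by these factors, or that the curve will rise while no titer rises. The documents support neither. The factors rest on assumed titer ratios and departure patterns, and a rise needs strong selection or slow waning. A distorted slope is the general risk. The change is worth making because it is cheap and serves a stated aim of these cohorts.

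**What to change.** In SAP 6.5.1 and 6.5.2, for Cohorts 11–13:

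1. For each visit after Day 50 (Days 85, 184, 365, 547, 730), add the ratio of the titer to the same subject's Day 50 titer, as geometric mean with t-based 95% CI, by cohort and by enrolment age group. The existing rule that CIs need at least 3 subjects can apply.
2. Show n under each point of the GMT and GMFR line plots.
3. Label both lines as based on a changing set of subjects.

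Optional sensitivity analysis: a repeated-measures model of log titer on all data up to the outside vaccination, with the missing-at-random assumption stated. In the simulation with about 1.3-fold waning and low-titer departure, a missing-at-random estimate gave 199/150/115/91 against a true 199/149/112/85. The covariance must be parsimonious: Table 8 has 12 immunogenicity visits, so an unstructured matrix has 12 × 13/2 = 78 parameters, while Cohorts 11 and 13 have 30 subjects each before any departure.

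Cost: one further table per cohort and edits to existing figures, all from data already collected; the model is extra work. Downside: late ratios will rest on few subjects, and they remove selection on titer level but not on waning rate. If half the subjects fall two-fold and half four-fold, and the latter leave, the ratio reads 0.50 against a true 1/√8 = 0.35.
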